o HIV Disease Control Status (unable to initiate therapy; on therapy-HIV controlled; on therapy-HIV not controlled; documented treatment failure; other), viral load suppression (Y/N) [SO]; a dummy variable noting whether the patient was defined as lost-to-follow-up (no contact w/patient > 2 months); and a variable noting persistence of attendance (# of appointments attended in each quarter of the prior year) [SO].

Family History of Substance Abuse 3 questions

o Monthly clinic data for patients will be coded from 6 months prior to accrual into the study until 18 months follow-up.

STAFF Questionnaires are given to the staff who receive the teaching intervention in 2015. There are 2 instruments to measure staff stress related to caring for persons with HIV disease.

2 *Upload a copy of all questionnaires/surveys:

Name	Created	Modified Date
ADDITIONAL questions STAFF.docx	7/21/2016 12:13 PM	7/21/2016 12:13 PM
Staff Questionnaire_v8.26.15. clean copy.doc	8/26/2015 10:18 AM	8/26/2015 10:35 AM
Patient Follow-upSurvey1_v7.7.15	7/7/2015 4:44 PM	7/7/2015 4:44 PM
Patient Total Survey v7.7.15	7/7/2015 4:43 PM	7/7/2015 4:43 PM
Patient Total Survey v5.5.15	5/11/2015 1:27 PM	5/19/2015 11:31 AM
Staff Questionnaire_v11.2014-2.doc	12/1/2014 1:26 PM	12/1/2014 1:26 PM
FINAL_Family History of Substance Abuse (2).docx	10/14/2014 6:57 PM	10/14/2014 6:57 PM
Patient's Total Survey_v6.27.14	7/2/2014 1:02 PM	7/2/2014 1:02 PM
POS_Touch Pad	7/2/2014 1:01 PM	7/2/2014 1:01 PM
Burnout inventory	5/16/2014 1:11 PM	5/16/2014 1:11 PM
AIDS Stress Scale	5/16/2014 1:11 PM	5/16/2014 1:11 PM
FAMCARE Scale.pdf	12/19/2013 4:40 PM	12/19/2013 4:40 PM
Sexual-Behaviors.pdf	12/19/2013 4:39 PM	12/19/2013 4:39 PM
Health Care Power of Attorney.pdf	12/19/2013 4:34 PM	12/19/2013 4:34 PM
POS.pdf	12/19/2013 4:34 PM	12/19/2013 4:34 PM
McGill-QOL.pdf	12/19/2013 4:34 PM	12/19/2013 4:34 PM
Rosenberg Self-Esteem Scale.pdf	12/19/2013 4:34 PM	12/19/2013 4:34 PM
Alcohol-Drug-Use_Mental-Illness.pdf	12/19/2013 4:34 PM	12/19/2013 4:34 PM
Life-Events-Checklist.pdf	12/19/2013 4:33 PM	12/19/2013 4:33 PM
AACTG_Adherence.pdf	12/19/2013 4:33 PM	12/19/2013 4:33 PM
HIV Symptom Index.pdf	12/19/2013 4:33 PM	12/19/2013 4:33 PM
ECOG Performance Status.pdf	12/19/2013 4:32 PM	12/19/2013 4:32 PM
Demographics.pdf	12/19/2013 4:32 PM	12/19/2013 4:32 PM

3 *What is the total length of time that each survey is expected to take?

The STAFF Questionnaires take less than 5 minutes to complete.

The PATIENT questionnaires initially take 45-60 minutes to complete but the same questions will be repeated at 2 subsequent data collection times and, in our

experience, responders take about half this time to complete the questions in future surveys.

4 * Are any of the questions likely to cause discomfort in participants or cause harm if their confidentiality were breached? (i.e., Illegal activities)
 Yes No

5 * Do any questions elicit information related to the potential for harm to self or others?
 Yes No

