The study uses a quasi-experimental design with pre-tests and post-tests for staff being trained. It provides a control group to directly compare the effects of the educational intervention upon the management of patients by measuring responses of patients before and after the staff is, or is not, trained. The Intervention Group (Clinic 1) and Control Group (Clinic 2) are non-randomly assigned. Both clinics agreed and looked forward to participating in the study, but one clinic had significant budget reduction that resulted in selection of the other clinic for the primary intervention. Ideally we would have used a cross-over design offering the intervention to the second site but the funding cycle for this proposal was reduced from 5 to 3 years and it is only feasible to offer one clinic the intervention. However, we intend to offer staff of the control site the palliative training at the end of the study period if the outcomes are shown to be beneficial. We will make a comparison of the two clinics at baseline to identify possible bias in the final analysis of data.

Following is a description of Study activities; at the end, the teaching intervention is described.

ITEMIZED RESEARCH ACTIVITIES: (See Timeline in Additional Documents)

The study is accomplished in 5 active phases with 3 desired outcomes: (A) staff will be able to use coping strategies as they integrate palliative skills with outpatient HIV care and treatment; (B) patients, specifically (YMSM), will be characterized in the era of successful ART with regard to mental health and quality of life; and (C) the curriculum, previously refined in international settings, will be re-adapted for use early in management of chronic illness in the US to engage and retain patients known to be difficult to keep in care.

PHASE 0:

Months 1-6

Usual study start-up activities including finalization of contracts, hiring of personnel, establishment of study offices, creation of the database and purchase of study materials.

PHASE 1: Patient Recruitment and Enrollment

Begins Month 7 of the study and continues through about Month 24.

A. STAFF: No staff are enrolled, taught or interviewed in the first Phase.

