B. YMSM: The consent process, enrollment, and baseline data collection takes place at two HIV clinic sites to describe the YMSM population in Baltimore. Patients are enrolled until 102 are enrolled at each site (85 are needed for analysis and the 102 allows for anticipated drop-out). Each patient completes 3 surveys approximately every 6 months at his regular clinic visit.

C. CURRICULUM Refinement: An initial curriculum is attached in ADDITIONAL DOCUMENTS. The educational team will continue to review, test, and incorporate elements of the curriculum being re-adapted for the US from international teaching efforts used in federally funded implementation efforts of HIV care and treatment. Site #1 will be the INTERVENTION SITE. Directors of Site #1 have chosen to have a day-long educational session for All-STAFF to be introduced to CASA Study activity. The curriculum is attached in ADDITIONAL DOCUMENTS prior to being offered to All STAFF participants.

PHASE 2: Staff Recruitment [NOTE this refers to CASA Team – the trainers to be trained]

Begins Month 13 (November, 2014) of the study.

A. STAFF – There are 2 types of STAFF participants: 1) CASA Team (Trainers) and 2) All STAFF who complete 2 surveys:

1. The CASA Team (Trainers) - Recruitment of the selected 5-8 member CASA Team made up of clinic STAFF trainers to receive the intervention: (1 physician or nurse practitioner; 2 nurses; 1 nursing assistant; 1 social worker or counselor; 1 outreach worker; and 1 administrative staff) at the intervention site. These will be selected by the clinic Administrative Team and the Research Team using the following criteria: all disciplines represented; each person chosen should have full understanding of how the clinic functions; each should be selected for leadership qualities and teaching or supervisory experience.

Participants are asked to avoid intentional sharing of study content to avoid contamination of the control site. for purposes of Staff at the control clinic will have the option to experience the training at the end of the study if it is shown to be beneficial.

B. YMSM: Enrollment and data collection continue as described in Phase 1.

C. Curriculum: Finalization of curriculum is on-going through-out the study as feedback from Site 1 is used for final revisions.

PHASE 3: Educational Intervention (See document attached in ADDITIONAL DOCUMENTS)

January-February, 2015

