Sample size calculations were made for logistic regressions predicting the likelihood of patients reporting viral suppression which indicates control of their disease (meaning that the patient is actually taking ART as prescribed). This is based upon the following assumptions: (1) improvement of 10% in patients reporting viral suppression by Follow-up #2 Survey among patients at Site 1 (experimental); (2) $1 - \beta = 0.8$; (3) $\alpha = 0.05$; and (4) $deff = 2.2$.

These analyses estimate the need for a total sample size of 170 (85 per site) at study end. Allowing for 20% attrition from Baseline to Follow-up 2 it will be necessary for us to accrue a total of 204 patients (102 at each site) in order to have a sufficient number of patients completing all 3 Patient Surveys. This number is higher than the number of patients we estimated to be required for the two-sample comparison of survivor functions using Cox Proportional Hazard regressions ($n=140$), (176) allowing for attrition. This sample size provides adequate power for the proposed longitudinal regression models. Based upon analyses made with N-Query Advisor 7.0 software 44 assuming $\alpha = 0.05$ and power $(1 - \beta) = 0.8$, the 170 cases completing Baseline, Follow-up 1 & Follow-up 2 will allow us to identify "small to medium" effects for the total model ($R^2 = 0.063$) and individual coefficients as well as a "medium" effect for up to each of 15 co-variates on R^2 (as small as 0.055) as outlined in Cohen (29).

The proposed sample size will allow us to estimate models including: a) a dummy variable noting the intervention arm, b) a term to correct for attrition bias, c) the baseline counterpart of the dependent (patient outcome) variable, and, d) a set of up to 12 relevant co-variates.

ENSURING ELIGIBLE PATIENTS:

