Second, through comparison of longitudinal data points, we will describe "change in time-varying patient characteristics", "stressors", "modifiers" and "outcomes".

"Attrition and balance" in key characteristics of the pre- and post-test groups will be assessed by comparing data from those completing: only baseline surveys; baseline and one follow-up; and baseline plus 2 follow-ups.

LOGISTIC REGRESSIONS: For viral suppression and other dichotomous potential correlates of study outcomes we will estimate several logistic regression models.

Given the longitudinal data collection with respondents repeatedly completing the same measures, patient reports for all measures are likely to be correlated. This violates the assumption of independence underlying logistic regression because it results in underestimates of standard error and therefore inaccurately increases the likelihood of rejecting the null hypothesis (Type-I error). To take into account higher intra-class correlation in the nested observations, we will use several generalized estimating equation (GEE) models with logit link.(167) The GEE model relates the marginal response $\mu_{it} = E(y_{it})$ to a linear combination of covariates by: $g(\mu_{it}) = x_{it}\beta$ and under logit link, $g(\mu_{it}) = \log(\mu_{it}/1-\mu_{it})$, where y_{it} is the indicator of viral status of the individual i at time t partner, and β 's are the estimated parameters. In this model specification, the covariance structure is treated as nuisance parameter. We will be using STATA 12, statistical software (147) for data cleaning and data analysis.

SURVIVAL ANALYSIS:

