Descriptive analyses of the training evaluation forms (to be developed following refinement of the curriculum and submitted to the IRB before being used with STAFF) completed by the teaching team or instructors, expert coaches, and HIV clinic staff including administrative staff during all 3 levels of the CASA training including quarterly all-staff educational sessions will be used to evaluate the training. This analysis will 1) confirm that topics and issues intended to be taught were presented including cultural issues; 2) document both consistency and completeness of the training; 3) identify unanticipated issues raised during the training; and 4) identify aspects of the training that need revision or expansion. These descriptive analyses represent what Cook, Cook and Mark (26) refer to as the "take" of the intervention, or how successful the training is at accomplishing what it intends. Participant insights will be used to suggest training revisions to improve the "reach", or scope of the training, success of implementation and overall effectiveness of the training for other settings. The "reach" describes both breadth and depth of the impact of the training. Attendance logs will document that all members of the team received the training.

We will use the RE-AIM framework [62] in analyzing the acceptability, feasibility, and impact of the CASA intervention. The RE-AIM framework focuses on the content and outcome of a training and guides examination of the clinics including the social, cultural, and care needs of the YMSM. The analysis focuses on essential training elements that foster implementation and sustainability of the training incorporating staff and patient perspectives.

LONGITUDINAL DATA ANALYSIS:

The third analysis is longitudinal and will examine trends of change in study outcomes that will describe potential correlates/mediators of change, as well as comparisons of change in study outcomes for both populations (STAFF and PATIENTS) and potential correlates between study arms. Thus we are able to determine training effect and analyze maintenance and sustainability of intervention effects. Assumptions will be checked with non-parametric alternatives. Appropriate multiple testing techniques (i.e., Bonferroni) will be applied as needed. Analyses will be conducted using SAS 9.3 or IBM SPSS Statistics v20.

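### With one clinic per arm, training and clinic cannot be separated, and the type I error of the planned training-effect test is uncontrolled and cannot be estimated

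*Combined protocol and SAP*

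**What the plan says.** **Design** (Justification, Objective, & Research Design, question 2). There is one intervention clinic and one control clinic: "The Intervention Group (Clinic 1) and Control Group (Clinic 2) are non-randomly assigned". The reason for the choice is given: "one clinic had significant budget reduction that resulted in selection of the other clinic for the primary intervention". The same section calls the study descriptive and quasi-experimental and plans a baseline comparison of the clinics.

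**Sample size** (Sample Size and Data Analysis, question 1). The inputs are a 10% improvement in reported viral suppression at Site 1 by Follow-up 2, 80% power, alpha 0.05 and a design effect of 2.2. No cluster unit, ICC or source is given for the 2.2. The result is stated as "These analyses estimate the need for a total sample size of 170 (85 per site) at study end". The models carry an arm dummy, the baseline value of the outcome, an attrition term and up to 12 covariates.

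**Analysis** (question 2). Under Logistic Regressions, the stated reason for allowing for correlation is that the same respondents answer repeatedly; "we will use several generalized estimating equation (GEE) models with logit link", and the model is indexed by individual and time. Under Survival Analysis, Cox models compare Site 1 with Site 2. Propensity terms are added to balance patient characteristics. Under Longitudinal Data Analysis, the conclusion for staff and patients is "Thus we are able to determine training effect".

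**The concern.** The arm dummy is also the clinic dummy. Whatever makes patients at one clinic fare differently from patients at the other (funding, staffing, space, management) enters the arm coefficient, while the standard error reflects only variation between and within patients. An ordinary difference between two clinics can then appear as a significant training effect with too narrow an interval.

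Two things make this more than theoretical. Allocation followed a clinic-level event, the budget reduction. And Study Procedures, question 1, reports administrative changes and lack of space at the intervention clinic during the study, so clinic conditions were not constant over time.

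The plan is already cautious about staff. There it gives non-random assignment as one of several reasons for limiting between-site comparisons to description. It does not carry that caution over to patients.

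**Working it through.** **1. The plan's own figure.** I tried to reproduce 85 per site, in case the arithmetic showed what the 2.2 stands for. It does not. For an absolute 10-point rise (two proportions, two-sided 5%, 80% power), multiplying by 2.2 gives:
- 0% to 10%: 74 × 2.2 = 163 per site
- 14% to 24%: 241 × 2.2 = 531 (rounded up)
- 40% to 50%: 388 × 2.2 = 854 (rounded up)

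The smallest one-sided value, without continuity correction, is 128. Without the 2.2, about 85 arises only at extreme rates (1% to 11%, or 89% to 99%: 88 per site). The baseline rate, the scale of the 10% and the sidedness are not stated, so the calculation cannot settle the meaning of the design effect.

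**2. Degrees of freedom for clinic variance.** Two clinics minus two arm means leaves 0. Declaring clinic as the GEE cluster would not help, with one cluster per arm.

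**3. Two readings of 2.2.**
- Clinic clustering, 85 patients per clinic: 1 + 84 × ICC = 2.2, so ICC = 1.2/84 = 0.0143.
- Repeated surveys, three per patient ("Each patient completes 3 surveys approximately every 6 months at his regular clinic visit"): 1 + 2 × rho = 2.2, so rho = 1.2/2 = 0.60.

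**4. Size when the standard error omits a variance inflation D.** For a nominal two-sided 5% test of an unadjusted contrast, size = 2 × [1 − Φ(1.96/√D)], with D = 1 + 84 × ICC.

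| Clinic ICC | D | True size |
|---|---|---|
| 0 | 1.00 | 5% |
| 0.005 (assumed) | 1.42 | 10.0% |
| 0.01 (assumed) | 1.84 | 14.9% |
| 0.0143 (2.2 read as clinic effect) | 2.20 | 18.6% |
| 0.02 (assumed) | 2.68 | 23.1% |

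Simulating the clinic reading gave 19% to 20%; a one-sided 5% test gives 13.4%. Simulating the repeated-survey reading, with standard errors clustered on patient and no clinic variance, gave 5.0% to 5.2%.

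**5. Allowing for baseline.** The plan adjusts for the baseline outcome and models residualized change. What then matters is clinic variation in change. For a simple pre-post contrast with ICC 0.0143, let c be the correlation over time of a clinic's effect and r the within-patient correlation:

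D = 1 + [2 × ICC × (1 − c)] / [2 × (1 − ICC) × (1 − r) / 85]

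| c | Size, r = 0 | Size, r = 0.6 |
|---|---|---|
| 1 | 5% | 5% |
| 0.8 | 7.9% | 12.3% |
| 0.5 | 12.3% | 21.9% |
| 0 | 19.0% | 33.2% |

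The documents give neither c nor r for any outcome.

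**The case against.** The plan is open about its design. It says the clinics were not randomized, explains the choice, calls the work descriptive and a proof of concept, and plans baseline comparison, propensity terms and adjustment for the baseline outcome. Baseline adjustment removes part of any stable clinic difference, and if clinic effects were constant over time the pre-post test would keep its 5%. All of that stands, and it is why no single error rate can be quoted.

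It does not rescue the test. Propensity scores balance measured patient characteristics; a clinic attribute that coincides with arm cannot be balanced. Baseline adjustment does not remove clinic-level change. It is also incomplete: with Month 13 as November 2014, training in January 2015 falls in Month 15, while enrollment runs to about Month 24, so late enrollees have post-training baselines.

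Two stronger readings are tempting. A reader might infer that the plan's own 2.2 establishes a 19% error rate. It does not: the 2.2 has no stated cluster unit, and repeated surveys are the only correlation the plan discusses. A reader might also infer that multiplying every standard error by √2.2 = 1.48 repairs the inference. With no degrees of freedom for clinic variance, no rescaling from these data gives a valid test. The 2.2 was also given for viral suppression only, and other outcomes may have different clinic ICCs.

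**Conclusion.** The structural point holds without any assumption about the ICC. Arm and clinic coincide, the planned GEE and Cox standard errors contain no between-clinic variance, and two clinics cannot provide it. The type I error of the training-effect test is therefore uncontrolled and not estimable from this study.

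The size is conditional. For an unadjusted two-sided 5% test it is about 19% if the 2.2 is wholly a clinic effect on the tested contrast. If the 2.2 is the repeated-survey effect, it is about 10%, 15% or 23% at assumed clinic ICCs of 0.005, 0.01 or 0.02. For a pre-post contrast at ICC 0.0143 it runs from 5% to about 33%, depending on how stable clinic effects are.

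Imprecision and bias should be kept apart. Wider intervals allow for ordinary clinic variation; they do not remove bias from a known difference between these two clinics such as the budget reduction.

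**What to change.** 1. **Define the design effect.** State whether 2.2 refers to clinics, repeated surveys or something else, with its ICC or correlation and source.
2. **Restate the claim.** In Longitudinal Data Analysis, replace the sentence about determining a training effect with a difference between two clinics, one of which was trained. Do not present the model p-value as a test of training.
3. **Add sensitivity intervals.** Report each site contrast over a stated range of assumed clinic ICCs. For an unadjusted contrast with 85 per clinic, ICCs of 0.005, 0.01 and 0.02 widen the interval by √1.42 = 1.19, √1.84 = 1.36 and √2.68 = 1.64. For baseline-adjusted contrasts, vary the assumed clinic variation in change. Label these as sensitivity, not as a correction, and use no single fixed multiplier.
4. **Add a placebo contrast.** Run the same site comparison on record-based attendance and viral load from calendar time before January 2015. Surveys/Questionnaires, question 1, codes monthly data from 6 months before accrual, so patients enrolled more than 6 months after training began have no pre-training months. Survival Analysis refers to 8 months before baseline; the two windows should be reconciled. The check may have limited power and cannot detect clinic changes after training began.
5. **State the remaining limits.** Name the budget reduction as a possible bias. Recruitment, question 1, and Informed Consent Process, question 6, say the two clinics were later combined; give the date and state this as a further limit on the contrast.

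The cost is changed wording, one added analysis on data the plan already collects, wider intervals and a more modest claim. The design is unchanged.

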The early implementation of a palliative approach is a complex interdisciplinary approach that enhances communication at the point of care and requires integration of attitudes and skills with comprehension of the underlying illness, in addition to operative disease-specific delivery models.(103,139) In this study, the experience from implementation of the CASA curriculum in HIV care and treatment in international settings is evidence of its value as a management model for chronic illness.(6,43,47) This approach encourages effective engagement in care and goal setting with patients and with family carers.(48) The proposed study is in line with the need for research to document the process of forming and training interprofessional care teams and represents an important advance in the field.(9) Large-scale studies of the early integration of a palliative approach have been impeded by multiple factors related to size and organization of services.(1) With greater than 50% of clinical events and deaths experienced by PLWH despite their use of ART, clinicians must be more attentive to symptom management; evidence of effectiveness of PC exists for other chronic illnesses.(5,50,71) Only 18-28% of ALL HIV positive individuals in the US have documented viral control,(148) with Baltimore ranking among the cities with the lowest percentage with viral control, with only 14% of HIV infected adults having documented viral control.(53) Chronic disease impacts the well being of patients, their families/informal support systems and professional caregivers(74) and the World Health Organization cited "patient-centered care" as one of four necessary health reforms.(165) Emphasis is placed upon the need for full integration of broader health and social needs to avoid neglecting holistic health promotion activities.(26) Symptom burden alone has been correlated with quality of life.(42) An international HIV review noted the need for integrated: 1) pain and symptom management; 2) advance care planning; 3) psychosocial support; and 4) delineated patient, clinician, and service delivery care barriers regardless of antiretroviral (ART) usage.(66) Regardless of whether a prior history of substance abuse exists, pain, a symptom commonly experienced with HIV, causes disability, suffering, and impaired QOL is poorly addressed.(37,38,55)

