This is a longitudinal, descriptive study evaluating the impact of an educational training for outpatient clinic staff on patient outcomes cared for by the trained staff members. The analyses are complex: 1) there are 2 target groups (staff and patients); and 2) the intervention is offered in 3 stages (teaching; coaching; all-staff education); and it is a pre-post comparison of the impact of a training intervention upon patients cared for by trained staff using 1 site as the control for the other.

The data collected is psycho-social, meaning both psychological and sociological, reflecting graded rather than dichotomous, or Yes-No responses. This means that multiple comparisons are being made. This large array of data requires mathematical modeling to describe true associations and accurate interpretation of the data. This is explained in detail below.

For PATIENTS quantitative results (survey responses) are supplemented by data extracted from the clinical electronic medical record (EMR) and by qualitative interviews with selected participants from each of the 2 target groups.

Addressing AIM 1: STAFF:

QUANTITATIVE: We will use data from Staff-Baseline and Staff-Follow-up surveys at both sites. We will enroll up to 80 STAFF members between the 2 sites. An array of descriptive and graphical techniques will be performed to characterize the distribution of the variables at each point in time as well as aggregate change in work-related stress, or burnout from Baseline (B) to Follow-up (F). Point estimates with confidence intervals will be used to estimate population values. Comparisons of data from participants in the Intervention and Control groups at Baseline (B) will identify potential heterogeneities between sites with regard to the distribution of staff background characteristics that might be related to stress or burnout (e.g., staff's clinic role/position -- physician, nurse, outreach worker, substance abuse counselor, etc.).

Between-group comparisons at B and F will be made with chi-square, t-tests (Fisher's exact as appropriate) and comparisons of change across time will be assessed by paired Student's t-test or paired Wilcoxon test. Post-hoc power calculations will be performed to determine if we have adequate statistical power for further testing.

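### The stated inputs (10% gain in viral suppression, power 0.8, alpha 0.05, deff 2.2) do not give 85 patients per site for the comparison with the control clinic

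*Combined protocol and SAP*

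**What the plan says.** Under Sample Size and Data Analysis, question 1 (SAMPLE SIZE), the calculation is for logistic regression of patient-reported viral suppression. The effect is "improvement of 10% in patients reporting viral suppression by Follow-up #2 Survey among patients at Site 1 (experimental"); the other inputs are power 0.8, alpha 0.05 and deff = 2.2. The result is "These analyses estimate the need for a total sample size of 170 (85 per site) at study end", raised to 204 enrolled for attrition.

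The section does not state a control or baseline suppression rate, whether the 10% is absolute or relative, the sidedness of the test, where the design effect comes from or what it multiplies, or any within-patient correlation. It does list "the baseline counterpart of the dependent (patient outcome) variable" among the model terms.

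Question 2 (DATA ANALYSIS) describes a pre-post comparison "using 1 site as the control for the other", so the effect of interest is a difference between clinics. Under LOGISTIC REGRESSIONS it adds: "To take into account higher intra-class correlation in the nested observations, we will use several generalized estimating equation (GEE) models with logit link".

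The only suppression rates in the documents are background figures under Supporting Literature: for Baltimore, "with only 14% of HIV infected adults having documented viral control", and nationally, "Only 18-28% of ALL HIV positive individuals in the US have documented viral control". Neither is a rate for the two study clinics.

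**The concern.** A 10-point difference between two proportions usually needs several hundred patients per group, and a design effect of 2.2 more than doubles that. Eighty-five per site is far below what the printed inputs suggest.

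This calculation sets the patient sample. A reader who accepts it will think that 85 completers per site can show or exclude a 10-point gain over the control clinic. At control rates of 14–28%, the expected 95% confidence interval half-width at Follow-up 2 is 12–14 points unadjusted and 8–11 points baseline-adjusted without the design effect, and 17–21 and 11–17 points with it. A true 10-point gain would often give an interval that includes zero, and a null result could be misread as evidence against the training.

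**Working it through.** **Inputs from the plan:** gain 0.10, read as absolute; power 0.80 (z = 0.8416); alpha 0.05; deff 2.2; 85 per site.

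**Assumptions, not in the plan:** two-sided test (z = 1.960); control rates of 14%, 18% and 28% from the background text. Rates of 50% and 70% are added because clinic patients may be better suppressed than the general HIV-positive population.

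**Step 1. Try to reproduce 85.** Per site, pooled formula:

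n = [1.960·√(2m(1−m)) + 0.8416·√(p₁(1−p₁) + p₂(1−p₂))]² / (p₂−p₁)², where m is the mean of p₁ and p₂; then multiply by 2.2.

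At 14% v 24%: m = 0.19, the roots are 0.5548 and 0.5503, so n = (1.0874 + 0.4631)² / 0.01 = 240.4, and 240.4 × 2.2 = 529.

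| Control v Site 1 | n, no deff | n × 2.2, pooled | n × 2.2, arcsine |
|---|---|---|---|
| 14% v 24% | 240 | 529 | 523 |
| 18% v 28% | 277 | 609 | 605 |
| 28% v 38% | 346 | 761 | 760 |
| 50% v 60% | 387 | 852 | 852 |
| 70% v 80% | 293 | 645 | 642 |
| 0% v 10% | 73 | 161 | 83 |

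The only near-match is the arcsine formula at 0% v 10% (or its mirror, 90% v 100%). That boundary is not a credible planning basis. Reading the 10% as relative makes matters worse: without the design effect, about 10,042 per site at 14% and 4,155 at 28%.

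**Step 2. Unadjusted power with 85 per site.** The design effect reduces 85 to 85/2.2 = 38.6. At 14%: (0.10·√38.6 − 1.0874)/0.5503 = −0.846, so power is 20%. With 85 it is (0.922 − 1.0874)/0.5503 = −0.301, so 38%. At 14/18/28%, power is 20/18/15% with the design effect and 38/34/28% without.

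**Step 3. Adjust for baseline suppression.** Simulated with 20,000 replicates, correlated binary waves with common correlation r, equal baseline rates, and a linear model with arm and baseline only. Type I error was 0.047–0.052. Two-sided power at 14/18/28%:

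| Analysis | r = 0.6 | r = 0.8 |
|---|---|---|
| Follow-up 2, no deff (85) | 54/49/41% | 73/70/64% |
| Follow-up 2, deff on patients (39) | 28/25/21% | 38/36/32% |
| Both follow-ups averaged, full gain at each, no deff | 71/64/55% | 85/82/78% |
| Both averaged, 5 points at Follow-up 1, no deff | 49/43/35% | 66/62/54% |

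A binary outcome that rises 10 points cannot have an arbitrarily high baseline correlation. At Site 1 the ceiling is 0.72 (14 to 24%), 0.75 (18 to 28%) and 0.80 (28 to 38%). Where a higher r is quoted, it holds at the control site and Site 1 is capped. At base rates of 50–70%, Follow-up 2 power without the design effect is 38–46% (r = 0.6) and 59–69% (r = 0.8).

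A logistic check at Follow-up 2 with r = 0.6 gave 57/50/42%, close to the linear figures. At r = 0.8 and a 14% base rate, two logistic runs disagreed (65% and 74%), so the r = 0.8 figures are approximate.

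**Step 4. What would give two-sided 80%?** Without the design effect, there are two routes at these rates:
- Follow-up 2 alone, with r of about 0.88–0.94.
- Both follow-ups averaged, with the full gain already present at Follow-up 1 and r of about 0.72–0.84.

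With the design effect on patients, even the best case at Follow-up 2 (nobody loses suppression, controls perfectly stable) gives 55–56%. Without it, the same best case gives 87–88%, falling to 74–75% if 1% of patients in each arm lose suppression.

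**The case against.** **Inputs may exist elsewhere.** A research plan is listed under Additional Documents but is not available. It may give the control rate, sidedness and correlation. This stands: what is shown is that the printed inputs do not yield 85, not what the true power is.

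**The design effect may refer to repeated surveys.** The GEE text makes this plausible, since 1 + (3−1) × 0.6 = 2.2, but that is an inference. On this reading r = 0.6, and two-sided power at 14–28% is 41–54% at Follow-up 2 or 55–71% averaging both follow-ups. Treating three survey waves as 255/2.2 = 116 per site gives 37–49% unadjusted. None reaches 80%.

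**The hypothesis is directional.** One-sided, without the design effect and averaging both follow-ups, power is 67–81% at r = 0.6 and 87–91% at r = 0.8. The section does not state a one-sided test, and with the design effect on patients the highest one-sided value for r up to 0.8 is 64%.

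**A pre-post test within Site 1 can reach 80%.** Without the design effect, a 10% gain with no losses gives 86% (exact McNemar), and a 12% gain with 2% losses gives 73%. This is not the controlled comparison that the plan describes.

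**The study is a proof of concept.** The plan also justifies its size by balancing interpretability against available cases and resources, and viral suppression is one of several outcomes. This argues against asking for more patients. It does not support an explicit 80% power claim.

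A reader might infer that averaging both follow-ups is the only way to 80%. It is not: Follow-up 2 alone gets there at a high enough correlation. Averaging is one route.

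**Conclusion.** The 85 per site does not follow from the stated inputs for the comparison between clinics. With the design effect on patients and a two-sided test, the requirement is about six to nine times larger at control rates of 14–28% (529/85 = 6.2; 761/85 = 9.0). Away from the 0% or 100% boundary, no control rate rescues it. Two-sided 80% power at 14–28% depends on dropping an input that the section states and adding a high correlation that it does not.

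The size of the shortfall rests on assumptions: 10 absolute points, a two-sided test, background rather than clinic suppression rates, and a simplified linear model without the other covariates, propensity term or attrition term. A reader might conclude that the study's true power is 15–20%. The documents do not support that, because the baseline-adjusted analysis does better and several inputs are unstated.

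Minor note: the section reports detectable "effects for the total model ($R^2 = 0.063$) and individual coefficients" without the number of predictors. At n = 170 that R² gives 81% power with 3 predictors but 49% with 15, for which about 0.107 is needed.

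**What to change.** In the SAMPLE SIZE text:

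1. State the control rate, absolute or relative scale, sidedness, the source of the design effect and what it multiplies, and the within-patient correlation. If the research plan holds these, repeat them here.
2. Replace the 80% claim for a 10-point gain with the power and detectable difference that 85 completers per site give for the baseline-adjusted between-site comparison. For example:

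> Assuming control rates of 14–28% (background figures, not clinic data), two-sided alpha 0.05 and 85 completers per site, power for a 10-point between-site difference at Follow-up 2, adjusted for baseline suppression, is about 41–54% at within-patient correlation 0.6 and 64–73% at 0.8 without a design effect, and 21–28% and 32–38% with a design effect of 2.2 on patients. The detectable difference at 80% power is about 14–17 and 11–13 points without it, and 22–25 and 19–21 points with it. Figures come from a linear model with arm and baseline only, not the full logistic/GEE model. Where 0.8 is quoted, the Site 1 correlation is capped at 0.72, 0.75 and 0.80 for control rates of 14%, 18% and 28%.

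3. If both follow-ups are to be averaged, say so and give those figures, with the assumed gain at Follow-up 1.
4. Commit to reporting the between-site difference in viral suppression with a 95% confidence interval, and state that a null result will not be read as evidence against the training.
5. Minor: give the number of predictors behind R² = 0.063.

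The cost is rewording one section and one short calculation. The stated power becomes less favourable. No extra patients, visits or data are needed.
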